The target population for this trial is treatment-seeking Veterans with Insomnia from the Durham Veteran's Affairs Healthcare System. Because few VA PCPs routinely document insomnia in the medical record⁷⁹, identifying patients with insomnia in the EHR is challenging. Prescribed sleep medications are the most common PCP response to an insomnia complaint, although some patients are referred for CBTI. Consistent with the larger literature, we found no difference between Veterans prescribed sleep medications and those who were not prescribed sleep medications in terms of improvements in insomnia severity ($f=.15$, $p=.70$) following participation in group based CBTI at the Durham VAMC⁸⁰. Thus, we have defined treatment-seeking Veterans with Insomnia as those who are: a) prescribed sleep medications; b) diagnosed with insomnia; or c) referred for clinic-based CBTI (but not yet treated).

Table 1. Eligibility Criteria Assessment: Methods and Measures

Eligibility Criteria	Assessment Method
Level 1 (L1)-Data Pull and Chart Review	
Inclusion	
≥ 18 years of age	EHR data pull
Insomnia Diagnosis OR prescribed sleep medications OR referred for CBTI	EHR data pull & record review
Exclusion	
Psychotic DO; Bipolar DO; Substance Use; Alcohol Abuse	EHR data pull
Dementia; Cognitive Impairment; Epilepsy; Seizure DO	EHR data pull
Severe OSA with treatment non-adherence	EHR record review
Unstable housing and/or no/unreliable telephone	EHR record review
Unstable Co-morbid Sleep DO; and current or prior participation in CBTI	EHR record review
No current/prior CBTI participation	EHR record review
Nursing Home Residence	EHR record review
Level 2 (L2)-Phone Screening, Consent & Enrollment	
Inclusion	
Insomnia Disorder diagnostic criteria are met per ICSD-3	DSISD Insomnia DO Module ⁶
Insomnia Severity Index score of ≥ 10	ISI ⁷
Exclusion	
Severe OSA with treatment non-adherence (when unclear from EHR review)	Phone Screening
Unstable housing and/or no/unreliable telephone (when unclear from EHR review)	Phone Screening
Excessive daytime sleepiness	Epworth Sleepiness >15
Nighttime or Rotating Shift Work w/in the last year	Phone Screening
Confirm no current/prior CBTI participation	Phone Screening
Severe Depression and Suicidality	PHQ-8 >19 and/or SI
Current Recreational Drug Use	Drug Use Screener endorsed
Nursing Home Residence (to complement information from EHR chart review)	Phone Screening

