We are requesting a Waiver of Informed Consent and HIPAA Authorization to identify and contact potentially eligible Veterans using the processes described above. We are also requesting a Waiver of Written Informed Consent as this would be the only document connecting patients to this study. By using these approaches that involve both record reviews and pre-screening via telephone, we limit the degree to which ineligible Veterans are required to travel to the VA to determine their study eligibility. We believe that asking these questions presents only minimal risk to potential study participants while simultaneously reducing the burden of traveling to the VA to assess eligibility. All potential participants found to be eligible for the study, and expressing desire to enroll in the study, will first provide their verbal consent prior to collection of baseline measures.

C.5 Randomization

Following completion of the baseline assessment, study participants will be randomized to either Tele-Self CBT or HEC in a 1:1 ratio, resulting in 100 participants in each condition. To assure equivalency across conditions on important variables, randomization will be stratified by Insomnia Severity Index score (≤ 20 / > 20 : based on findings for Veterans in the VA CBT National Dissemination and presence/absence of a mental health disorder.

C.6 Participant Compensation

Since study participants will experience some inconvenience to participate in this study, they will be compensated in the amount of \$58 for each of 3 assessment periods. Study participants will receive an additional \$3 per day (up to \$42 for the 2-week period) for completion of sleep diaries. In sum, study participants may receive up to \$100 for each 2-week assessment period, for a total of \$300 for completion of all study procedures. As noted above, each assessment period involves tracking sleep and wearing the actigraphy device at home for a period of 2 weeks and completing questionnaires by telephone.

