The study coordinator will inform patients of randomization arm at the end of the baseline. The various time points have windows in which the assessment period should be completed in. Participants may start the baseline assessment up to a month after consent. The 8-week assessment can start as soon as 6 weeks after starting the intervention period (if all nurse phone calls are completed) to no later than 8 weeks after intervention period has started. Participants have a 5-week window to start and complete baseline and 8-week assessment activities. Participants have a 6-week window to begin and complete 6-month assessment activities.

Covariate and Other Measures: Due to their established association with sleep, the following variables will be evaluated as potential covariates and included in analyses as appropriate: age; gender; body mass index (BMI); co-morbid medical conditions; co-morbid mental health conditions; smoking status and pack years; anxiolytic/hypnotic usage; and other medications. Self-report information about demographic characteristics and current medical and mental health conditions will be collected at baseline. During the 8 week and 6-month Assessments, we will ask participants in the Tele-Self CBT condition if they have sought or received treatment for their sleep complaints beyond what was offered in this study.

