C.9 Missing Data: Because the main predictors of interest are collected at baseline, we do not anticipate much missing data in these variables. We do, however, anticipate some missing values in the longitudinal outcomes owing to dropout or, rarely, patients not completing the sleep diaries or returning Actiwatches. Although we did not lose any Actiwatches in our pilot study, participants did not return 2 of 162 devices (1%) in a past trial⁴. If the missing values are related to other measured patient factors, such as age, comorbidities, or employment status (as we have seen in previous studies), then multiple imputation (MI) provides a framework for incorporating information from these auxiliary variables while still preserving a parsimonious main treatment effect mode. This framework is described as a significant advantage in recommendations from the Panel on Handling Missing Data in Clinical Trials. Depending on the type and scope of missing data for other longitudinal variables, as a sensitivity analysis, MI will be conducted via the SAS procedure PROC MI or the SAS macro IVEware. A general linear model for each outcome variable will then be applied to each of the imputed datasets, and estimates combined using Rubin's rules as implemented in PROC MIANALYZE.

Table 4. Contacts with Participants

STUDY CONTACTS			
Week#	Purpose of Contact	Measures	Time Commitment/Contact Modality
0	TELEPHONE-BASED SCREENING	Shift Work Question Drug Use Screener Prior participation in CBTI Question DSISD Epworth Sleepiness Scale Insomnia Severity Index PHQ-8	30 minutes/phone call
0	CONSENT AND ENROLL		20 minutes/telephone
2	BASELINE ASSESSMENT 
 ○ Participant calls IVR sleep diary system daily for 2 weeks ○ At end of 2 weeks, participant completes baseline questionnaires by phone ○ Following questionnaire completion, participant is randomized and informed of assigned treatment arm by phone 	Adverse Events Demographic and Service Information Comorbidity Questionnaire Insomnia Severity Index (ISI) Multi-Dimensional Fatigue Inventory (MFI) Morning Eveningness Questionnaire (MEQ) Pittsburgh Sleep Quality Index (PSQI) Glasgow Insomnia Index IPAQ short phone (physical activity) Insomnia Treatment Knowledge Questionnaire Sleep Medication Question COVID questions	5 minutes daily/IVR 40-50 minutes/phone call

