Study tracking data will be securely stored in a SQL server database created for this project. Members of the study team will be granted role-based permissions to connect to the database to enter, view, and update data using a Microsoft Windows tracking application created and supported by the Durham HSR&D software development team. We have used this tracking software for multiple prior studies. Because many processes for identification, enrollment, and follow-up of participants are similar to prior studies, we can easily customize the database and software to meet the specific needs of the proposed project. The database allows us to track: the status of each patient (eligible, enrolled, refused, etc.), results of medical record reviews, results of screening interviews, and all tasks due for each participant (e.g., follow-up assessments). We are also able to randomize participants within this database, as the randomization sequence and necessary stratification variables can be imported. Customized reports allow the research team to identify daily tasks in need of completion, as well as flow charts to monitor overall study progress. Screening and outcome measures (except for the sleep diary and actigraphy data) will be defined and entered using REDCap™, a web-based survey tool also running on a secure server behind the VA firewall. The REDCap software is a web-based survey tool running on HSR&D computer systems operated by VA OI&T personnel on behalf of HSR&D. At no time will the email function in REDCap be used for this project. Only data can be entered into this web-based survey tool. The data is stored on the servers at HSR&D and the coordinators and master statistician will have access to the raw data. The

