an unstructured covariance matrix to take into account the within-patient correlation between repeated measures over time. The predictors in the model will include a dummy coded time effect and an indicator variable for Tele-Self CBT interacting with the time effect. The mean structure of the model will have the form: $Y = \beta_0 + \beta_1 * 6\text{wk} + \beta_2 * (\text{month6}) + \beta_3 * (\text{Tele-Self CBT1} * 6\text{wk}) + \beta_4 * (\text{Tele-Self CBT1} * \text{month6}) + \beta_5 * (\text{age}) + \beta_6 * (\text{baseline ISI})$, and model parameters will be estimated using the SAS procedure MIXED (Cary, NC). Note that this model is a constrained intercept model, which assumes a common baseline mean¹⁰⁹. We will formally evaluate the intervention effect by testing that β_3 differs from zero and report the mean difference and corresponding 95% confidence interval. A mean difference significantly less than zero provides evidence that Tele-Self CBT patients have greater improvements in ISI at 8 weeks. The model will also include centered, stratification variables of age ($\leq 50/ > 50$ years), baseline ISI ($\leq 20/ > 20$), *mental health disorder status (presence/absence)*, *psychotropic medication (use/non-use)* and *sleep medication (use/non-use)* as recommended in the CPMP guidelines¹⁰⁸.

Hypothesis 2: Relative to Health Education, participants randomized to receive Tele-Self CBT1 will have greater improvements in subjective sleep (per diary SOL, WASO, and SE), objective sleep (per actigraphy WASO, TST, and SE), fatigue, depression symptoms, and QOL at 8 weeks. As described above, sleep parameters (both diary and actigraphy) are recorded daily during each of the three 2-week assessment periods. Daily values will be averaged across each 2-week period, resulting in three repeated continuous outcomes for each of the sleep parameters, including baseline, 8 weeks, and 6 months. Treatment group differences at 8 weeks and 6 months for these subjective and objective sleep measures will be tested via the same general linear model as specified above for the primary hypothesis. Similarly, the fatigue, depression symptoms and QOL outcomes will also be analyzed with a general linear model as specified above for the primary hypothesis. Again, PROC MIXED will be used to estimate and test the appropriate model parameters, and the mean difference and corresponding 95% confidence intervals will be reported.

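### The primary ISI model leaves out the screening ISI, a second pre-randomisation score that every participant has; using it would narrow the confidence interval modestly

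*Combined protocol and SAP*

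**What the plan says.** **Two ISI scores before randomisation.** Table 4 lists the ISI in the week-0 telephone screen ("DSISD Epworth Sleepiness Scale Insomnia Severity Index PHQ-8") and again in the week-2 baseline assessment ("Comorbidity Questionnaire Insomnia Severity Index (ISI) Multi-Dimensional Fatigue Inventory (MFI"). Table 1, Level 2, makes an "Insomnia Severity Index score of ≥ 10" an entry requirement, so every randomised participant should have a screening score. The two scores are separate measurements. Section C.8 says "Participants may start the baseline assessment up to a month after consent", and Table 4 places the baseline questionnaires at the end of two diary weeks. Section C.5 puts allocation after both: "Following completion of the baseline assessment, study participants will be randomized to either Tele-Self CBT or HEC in a 1:1 ratio".

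**The screening score is kept.** Section E says "Screening and outcome measures (except for the sleep diary and actigraphy data) will be defined and entered using REDCap", and that REDCap results are linked by study identifier for analysis.

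**The model.** Section E.2, Hypothesis 1: "The predictors in the model will include a dummy coded time effect and an indicator variable for Tele-Self CBT interacting with the time effect". It adds age, baseline ISI, and centred terms for age group, baseline ISI (≤20/>20), mental health disorder, psychotropic medication and sleep medication. The covariance is unstructured and the baseline mean is common to the arms. The screening ISI is not in this model and not on the candidate covariate list in section C.8. No reason is given.

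**The stratum.** Section C.5 says "randomization will be stratified by Insomnia Severity Index score" without saying which measurement. Section E.2 calls it baseline ISI.

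**The concern.** A single ISI is a noisy reading of a person's severity; the plan's own repeated-measures correlation is 0.6. A second score taken before randomisation will usually say something about the 8-week ISI that the first does not. Both scores precede allocation, so adjusting for both does not bias the randomised contrast. It can narrow the reported interval with no extra patients, calls or questions.

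At stake is precision only: the width of the 95% confidence interval for the primary effect, and power if the true effect is smaller than planned. Section E.3 itself expects a smaller effect than in-person CBTI, against a comparator that receives more than usual care.

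**Working it through.** **Inputs from section E.3:** SD 5.8, repeated-measures correlation 0.6, type I error 5% (two-sided per section E.1), 90% power, 73 per arm, 100 per arm randomised, difference given as both 2.8 and 3.

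**Step 1: reproduce the plan's figure.** With variance factor v, n per arm = 2·v·5.8²·(1.96 + 1.28)²/δ². A change score has v = 2(1 − 0.6) = 0.80.

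- δ = 2.8 gives 72.1, so 73. This matches.
- δ = 3 gives 62.8, so 63. The 73 therefore belongs to 2.8.

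**Step 2: variance factor with one and two baselines.** Let rb and rs be the correlations of baseline and screening ISI with 8-week ISI, and rbs the correlation between the two.

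- Baseline only: v = 1 − rb² = 1 − 0.36 = 0.64.
- Both: v = 1 − (rb² + rs² − 2·rb·rs·rbs)/(1 − rbs²).
- All three at 0.6: v = 1 − (0.36 + 0.36 − 0.432)/0.64 = 0.55. The variance falls by 1 − 0.55/0.64 = 14%.

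The documents give one correlation and do not give rs or rbs. Those are assumptions in the table, with rb = 0.6 throughout.

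| rs | rbs | v with both | Variance reduction, no selection |
|---|---|---|---|
| 0.60 | 0.6 | 0.550 | 14.1% |
| 0.60 | 0.7 | 0.576 | 9.9% |
| 0.60 | 0.8 | 0.600 | 6.3% |
| 0.55 | 0.7 | 0.607 | 5.2% |
| 0.55 | 0.8 | 0.626 | 2.1% |
| 0.50 | 0.8 | 0.639 | 0.2% |

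**Step 3: allow for selection.** Entry at 10 or above narrows the range of the screening score. This was simulated with whole-number ISI scores, SD 5.8, an assumed mean of 15 to 19, truncation at 10, and the ≤20/>20 term already in the model.

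| rs | rbs | Stratum from baseline ISI | Stratum from screening ISI |
|---|---|---|---|
| 0.60 | 0.6 | 10–12% | about 5% |
| 0.60 | 0.7 | 8–9% | about 4% |
| 0.60 | 0.8 | 5–6% | about 3% |
| 0.55 | 0.7 | 4–5% | about 2% |
| 0.55 | 0.8 | about 2% | about 1% |
| 0.50 | 0.8 | about 0.2% | about 0.1% |

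With a wider range of assumed means (14 to 20), the screening-stratum figure at rs = 0.6 runs from about 3% to 6%.

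**Step 4: effect on the interval and on power.** SE = 5.8·√(2v/n), ignoring selection. The second line of each pair is the best case, with all correlations 0.6.

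| n per arm | Baselines | v | SE | 95% CI half-width | Power at 2.8 |
|---|---|---|---|---|---|
| 73 | One | 0.64 | 0.768 | 1.51 | 95.4% |
| 73 | Two | 0.55 | 0.712 | 1.40 | 97.6% |
| 100 | One | 0.64 | 0.656 | 1.29 | 98.9% |
| 100 | Two | 0.55 | 0.608 | 1.19 | 99.6% |

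For a true effect of 2.0 points, which is an assumption and not a planning value, best-case power rises from 74% to 80% at 73 per arm and from 86% to 91% at 100 per arm.

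**The case against.** **The planned analysis is already adequate.** Adjusting for one baseline of the outcome plus strata is a conventional primary analysis, and power at the planned 2.8 points is ample. This stands. A reader might infer that the omission biases the effect, inflates type I error or leaves the trial underpowered. The documents support none of these: the model as planned does not need the screening score to be valid, and Step 4 shows about 95% power at 73 per arm without it.

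**The gain is uncertain and probably below 14%.** This also stands. Screening and baseline lie a few weeks apart with no study treatment between them, so they may well correlate above 0.6. The screening score is further in time from week 8, so it may correlate below 0.6 with that outcome. Both shrink the gain. Other covariates in the model may take up part of it too. The omission is certain; the size of the benefit is not.

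**The stratum may already carry the screening score.** Section C.5 leaves this open. If it does, a dichotomised form is in the model and only a smaller increment remains.

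**The same change might seem to apply to the screening PHQ-8 in the depression model.** The documents do not support that as they stand. Table 3 and section F.3 place a PHQ-8 at baseline, but Table 4 omits it from the week-2 list. If the screening score serves as the baseline, adding it would duplicate a term.

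**Conclusion.** The point holds as a missed efficiency. Every participant has, by design, a second pre-randomisation measurement of the primary outcome, and the Hypothesis 1 model does not use it. The expected reduction in the variance of the 8-week effect is roughly 0–12% after selection, or about 1–6% if the stratum is the screening score (close to nothing under the weakest correlations tried). A 12% reduction would take the 95% CI half-width at 100 per arm from 1.29 to 1.29·√0.88 = 1.21 ISI points; a 2% reduction would leave it at about 1.27.

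These sizes rest on the plan's SD and 0.6, on assumed values for the two unreported correlations, and on an assumed mean screening ISI of about 15 to 19. The benefit is a modestly narrower interval and some extra power for effects below 2.8. No conclusion at the planned effect depends on it.

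**What to change.** Before unblinding, amend section E.2, Hypothesis 1, in one edit:

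1. Add screening ISI (continuous, centred) as a covariate with its own slope at each modelled time point, including baseline if baseline ISI stays in the response vector. Enter it as a covariate and not as a further response, because participants are selected on it.
2. State whether baseline ISI is a response (constrained baseline mean) or a covariate. The printed model has it in both roles, and the new term cannot be specified until this is settled.
3. State which ISI measurement defines the ≤20/>20 stratum, and use the same wording in sections C.5 and E.2.

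For the depression model, first reconcile Table 3 and section F.3 with Table 4 on whether the PHQ-8 is given at baseline. Add the screening PHQ-8 as a further covariate only if a separate baseline PHQ-8 is collected.

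The cost is a short SAP edit and two or three degrees of freedom. The sponsor should also confirm that the screening score, taken before verbal consent, may be kept as analysis data for those who enrol. No new data collection is needed.

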E.1 Data Summary (Aims 1 & 2): Descriptive statistics, including graphical displays, will be used to summarize all study variables, both overall and by intervention group. Evidence of imbalance in baseline characteristics will be noted and discussed as to whether they are clinically significant. As recommended by Committee for Proprietary Medicinal Products¹⁰⁸ guidelines, we will consider sensitivity analyses adjusting for these baseline characteristics to ensure that an observed intervention effect is not due to baseline imbalance. Trajectory plots and frequency distributions will be used to explore longitudinal outcomes. We do not anticipate substantial deviations from symmetric, normal distributions for the study outcome variables. Additionally, correlation patterns over time, both overall and by intervention group, will be examined via scatter plots. The main conclusions drawn from this trial will be based on the pre-specified primary and secondary hypotheses outlined below and will be tested with two-sided p-values at the standard 0.05 level. All statistical analyses will be performed using the SAS software package (Cary, NC); the Durham HSR&D Center of Innovation maintains the current SAS release on the Durham VA hospital servers.

E.2 Intent to Treat Analyses (Aims 1 & 2): All primary and secondary analyses focus on the effect of the intervention compared to control. We, therefore, plan to use the intent-to-treat assumption for all analyses; participants will be analyzed as part of the group to which they are randomized, regardless of intervention adherence.

Hypothesis 1: Relative to Health Education, participants randomized to receive Tele-Self CBT will have greater improvements in insomnia severity, as measured by the Insomnia Severity Index (ISI), at 8 weeks. The ISI is a continuous measure wherein lower scores indicate less severe insomnia symptoms. A general linear model will be used to estimate changes in ISI over time and test the primary hypothesis. Because of the small number of time points, we will apply

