E.3 Sample Size Considerations (Aims 1 & 2): Our sample size estimates are based on the Hypothesis 1 primary outcome – Insomnia Severity Index. Because this is a longitudinal study with repeated measurements on each subject, mean change is estimated with increased precision. In sample size calculations, the increase in precision can take into account the correlation between repeated measures. With Tele-Self CBT1, we anticipate seeing smaller effects than might be seen with in-person CBT1. Additionally, our comparison group receives more than usual care, again leading to smaller effects. In a recent meta-analysis, the effect of CBT1 on ISI yielded large Hedge's g effect sizes of 0.98. Conservatively, we then base our sample size estimates on an effect size of 0.5; this translates into a relative mean improvement on the ISI of at least 2.8. Assuming a baseline SD of 5.8, a repeated-measures correlation of 0.6 (both quantities estimated from previous studies^[37,52,54,114]), and a type-I error of 5%, we will need to have 73 patients in each arm to detect a relative mean improvement of 3 on the ISI with 90% power. To account for dropout and possible deviations from our assumptions, we plan to enroll and randomize 100 patients in each arm (total sample size n=200). With this sample size, we will also have adequate power to examine our secondary outcomes. For example, previous studies of SE show a baseline SD of 12.5 and repeated-measures correlation of 0.7. With our projected sample size, we will have 90% power to detect a relative improvement in SE of at least 6.2. The repeated-measures design option in PASS¹¹⁵ was used for all calculations.

E.4 Data Analysis (Aim 3)

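### The primary ISI model uses baseline ISI both as a response and as a covariate with one coefficient for all visits, so its mean structure is mis-specified

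*Combined protocol and SAP*

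**What the plan says.** Section E.2, Hypothesis 1, gives a mean model for ISI with an intercept, dummies for the two follow-up visits (the first labelled 6wk, although the hypothesis concerns 8 weeks), treatment only through its interactions with those dummies, a term β5 for age and a term β6 for baseline ISI. The covariance is unstructured, the fit is by PROC MIXED, and the primary test is of β3. The plan adds: "Note that this model is a constrained intercept model, which assumes a common baseline mean". Baseline is therefore the reference visit and a row of the response. Hypothesis 2, which uses the same model, confirms three repeated outcomes including baseline.

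E.2 continues: "The model will also include centered, stratification variables of age", and the list that follows includes baseline ISI split at 20. In C.5, "randomization will be stratified by Insomnia Severity Index score", with the same split. No baseline ISI by visit term appears anywhere.

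**The concern.** Adjusting for a stratification factor is normally sound. Here, however, the factor is a cut of one of the response rows. The difference between the >20 and ≤20 groups is largest at baseline, where the groups are defined, and shrinks at follow-up whenever the correlation between visits is below 1. A coefficient without a visit interaction cannot represent both gaps. The residual covariance absorbs the misfit, and that covariance determines the standard error of β3 and how the model compensates for missing follow-up.

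The equation itself shows no cut. If β6 multiplies the continuous score, the baseline row is regressed on itself, which is a more basic failure. Either way the affected quantity is the trial's only primary test and the confidence interval reported with it.

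**Working it through.** **Inputs.** From E.3: SD 5.8, correlation 0.6, 100 per arm. From E.1: two-sided 5% level. Assumed, because the documents do not give them: normal scores, baseline mean 19, and all dropout rates and patterns.

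**The plan's own figure.** With change-score variance 2 × 5.8² × (1 − 0.6) = 26.91 and a difference of 2.8, n = 2 × (1.960 + 1.282)² × 26.91 / 2.8² = 72.1, hence 73 per arm, as E.3 states. (The 3 points written beside 73 would give 62.8, hence 63.) The SD and correlation are thus the ones the plan used.

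**Stratum reading: the two gaps.** The cut lies at z = (20 − 19)/5.8 = 0.172, with density φ = 0.393 and Φ = 0.568. The baseline gap is 5.8 × (0.393/0.432 + 0.393/0.568) = 9.3 points. At 8 weeks it is 0.6 × 9.3 = 5.6. Fitted to a very large simulated sample, the single coefficient settles at 8.2, which is wrong at every visit.

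**Complete data: reported standard error.** Without the term, the 8-week variance given baseline is 5.8² × (1 − 0.6²) = 21.53, so SE = √(2 × 21.53/100) = 0.656. With the term, the fitted residual variances are 12.66 (baseline) and 27.67 (8 weeks), with covariance 6.73. The conditional variance is 27.67 − 6.73²/12.66 = 24.09, so SE = √(2 × 24.09/100) = 0.694. The variance ratio is 24.09/21.53 = 1.12.

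Simulation with permuted blocks of 4 within ISI stratum (4,000 trials under the null) shows that this extra width is not real:

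| Model | True SD of β3 | Reported SE | Null rejection | Power, 3 points |
|---|---|---|---|---|
| With ISI indicator | 0.662 | 0.694 | 3.8% | 99.4% |
| Without it | 0.660 | 0.656 | 4.9% | 99.6% |

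A separate simulation of 2,500 trials gave reported SEs of 0.692 and 0.654 and null rejection of 4.0% and 5.5%. The excess in reported variance ranges from 9% (correlation 0.7) to 16% (correlation 0.4). It is 9% when baseline is truncated to 10–28 to reflect the Table 1 criterion ("Insomnia Severity Index score of ≥ 10").

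**Why dropout can bias β3.** The fitted model implies that 8-week ISI rises with baseline ISI at slope 6.73/12.66 = 0.53, plus a step at the cut of 8.19 × (1 − 0.53) = 3.8 points. The data were generated with slope 0.6 and no step. The implied gap between strata at 8 weeks is 3.8 + 0.53 × 9.3 = 8.8 rather than 5.6. If the strata are depleted equally in both arms, the error cancels. If not, it enters β3.

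Large-sample bias in ISI points (150,000 per arm, no true effect), by logit slope of dropout per baseline SD:

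| Dropout pattern | 15% dropout | 25% dropout |
|---|---|---|
| Same slope in both arms | about 0 | about 0 |
| Slope 0.5, Tele-Self only | 0.10 | 0.17 |
| Slope 1, Tele-Self only | 0.18 | 0.31 |
| Slopes +1 and −1 (extreme) | 0.34 | 0.59 |

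With truncated baseline the last three rows span 0.09 to 0.31 at 15% dropout and 0.15 to 0.55 at 25%. The sign reverses when milder Tele-Self patients leave more often (−0.27 at slope −1, 25%). Without the term, or with stratum by time, the bias is 0.02 or less. At 100 per arm and 25% dropout, null rejection with and without the term is 4.5% and 5.1% (second row), 6.7% and 4.7% (third), and 12.2% and 5.6% (fourth).

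**Continuous reading.** The slope of baseline ISI on itself is 1, while the follow-up slope is 0.6. In one simulated trial the log-likelihood rose from −1776 at β6 = 0 to −1593 at 0.6, −855 at 0.99 and +66 at 0.9999, while the baseline residual variance fell towards zero. There is no maximum. For every fixed β6 below 1, β3 was the same and equal to the baseline-adjusted estimate, so what fails is the estimation; β3 itself is not biased.

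**The case against.** The strongest reply is that the certain harm is small and conservative: an interval about 6% too wide in a trial with more than 99% power would rarely change a conclusion. That is correct and limits the weight of the point.

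Second, bias needs dropout that depends on baseline ISI differently by arm. C.9 raises dependence on patient factors ("If the missing values are related to other measured patient factors, such as age, comorbidities, or employment status") but names neither ISI nor an arm difference, and call schedules are matched across arms. This also stands. Against it, only Tele-Self includes sleep restriction, so arm-specific dropout cannot be excluded beforehand, and E.3 allows for attrition without giving a rate; going from 73 to 100 per arm leaves room for 27%.

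Third, C.9 plans multiple imputation. With the indicator kept and follow-up imputed from baseline ISI and arm, the bias at 25% dropout fell from 0.28 to −0.01 (slope 1, Tele-Self only) and from 0.59 to 0.03 (opposite slopes). But that analysis is conditional and a sensitivity analysis; the primary estimate would still be the biased one.

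Fourth, ISI is also measured at screening (Table 4), and C.5 does not say which score defines the stratum. With a screening stratum the reported-variance ratio would be only 0.92 to 1.05, for assumed screening-to-baseline correlations of 0.6 to 0.9. E.2, however, says baseline ISI. Finally, the continuous reading is the less likely one, and its failure would show at the first fit. It would still force an unplanned change to the primary analysis.

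**Conclusion.** The point holds. As written, the primary model uses baseline ISI twice and is mis-specified on either reading of β6. On the likelier, stratum reading and with complete data, β3 is unbiased and power is adequate, but the reported SE is about 6% too large and the test slightly conservative. Bias arises only if dropout depends on baseline ISI differently by arm. In the one-arm patterns examined it is 0.10 to 0.31 points at 15% to 25% dropout, against a design difference of 2.8 to 3. Such dropout is missing at random given observed baseline ISI, and the constrained model handles it once the extra term is removed. On the continuous reading the model cannot be fitted. These sizes rest on SD 5.8, correlation 0.6, an assumed baseline mean of 19 and assumed dropout. The model should be corrected before analysis; the error does not undermine the design.

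**What to change.** Use baseline ISI once in the Hypothesis 1 model. Either of these does so:

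- Keep baseline as a response and delete both β6 and the ≤20/>20 indicator. The constrained model already adjusts for baseline ISI.
- Model only the 8-week and 6-month ISI, with continuous baseline ISI by time, and delete the constrained-intercept sentence. In simulation this matched the first option (true SD 0.659, reported SE 0.654).

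If the stratifier must remain visible in the primary model, enter it as stratum by time (reported SE 0.655, null rejection 5.0%). The SAP should also say whether the ISI stratum comes from the screening or the baseline score. For the other outcomes the indicator may stay as written: there it is not a cut of the response, and in a check it cost about 1% in SE, an amount that depends on how closely the outcome tracks ISI.

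The cost is SAP wording and one line of PROC MIXED code, with no extra patients or data. With variance 21.53 the required n is 2 × (1.960 + 1.282)² × 21.53 / 3² = 50.3, hence 51 per arm for 3 points, and 58 for 2.8. The planned 100 per arm remains sufficient.
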